The MITT analysis set will comprise all randomized participants. Missing data in the full analysis set will occur if participants discontinue treatment prior to the end of the study or do not complete an outcome measure. In general, participants will remain in the study unless consent is withdrawn or if there are concerns regarding participant safety. However, participants will be required to complete the full course of treatment (12 sessions) within a maximum of 18 weeks, in order to maintain the integrity of the treatments (Barlow et al., 2017). If participants fail to do so within 18 weeks, treatment will be discontinued and follow-up assessments will be completed. Missing data for the MITT analysis set will be accounted for using full information maximum likelihood (ML), which is superior to most alternative missing data approaches even when data is missing completely at random (MCAR) or missing at random (MAR; Schafer & Graham, 2002; Enders, 2010). Although the use of ML will result in the least biased parameters, regardless of data missingness, several approaches will be undertaken to better understand the exact mechanisms for missing data. Little's (1988) MCAR test will be applied to all final models to determine whether data can be considered MCAR. Further, the results of analyses using study completers and protocol adherers (completer and per-protocol analyses) will be compared with results using the MITT analysis set to test sensitivity of study conclusions to study discontinuations and protocol non-adherence. Baseline differences also will be explored between treatment completers and those that discontinue. If baseline differences are detected, these covariates will then be included in the final model as auxiliary variables to improve the plausibility of assuming data is MAR (Collins et al., 2001; Enders, 2010; Graham, 2003;). Finally, discontinuation proportion will be used as one of the outcome measures of intervention feasibility.

Efficacy Measures Analyses (Primary Aim)

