17. *SAFE-TBT*. The SAFE-TBI was designed to identify the level of evidence for exposure to mild TBI (McAllister et al., 2016). The SAFE-TBI includes a definition of mild TBI as well as three multi-part screening questions, regarding: 1) exposed to, screened for, or put on restricted duty due to any head or brain injury from six examples (e.g., blast or explosion); 2) associated symptoms that occurred immediately after the head or brain injury (e.g., duration of loss of consciousness, feeling dazed or confused, amnesia); and 3) memory loss of events just before or after the injury. The SAFE-TBI has demonstrated moderate levels of agreement for inter-rater and test-retest reliabilities (McAllister et al., 2016). In addition, the SAFE-TBI demonstrated reasonable convergent validity with more extensive measures of TBI in a VA sample.
18. *Veterans Short-Form Health Survey (V/SF-36)*. The V/SF-36 is a 36-item measure designed to assess functional health, well being, and quality of life in Veterans, and can be scored to produce two primary subscales for physical health and mental health (Kazis, 2000). The V/SF-36 was adapted from the original SF-36, which has received extensive support in the literature (Ware & Sherbourne, 1992).

Participants will be asked to complete the assessment materials four times throughout the duration of treatment: pre-treatment, mid-treatment (session 6), post-treatment and six-month follow-up. Participants also will complete select measures bi-weekly to monitor treatment progress.

Potential Risks

There is a potential psychological risk of emotional discomfort during the assessment and treatment procedures. Although this reaction is not uncommon in exposure-based treatments of anxiety and depression and typically is brief in its duration, there are several provisions to reduce and/or avoid it in the proposed study. First, the proposed treatments are designed specifically to target the reduction of emotional distress, anxiety, and

avoidance. Second, if a participant expresses a desire to discontinue treatment due to distress and/or a study clinician determines that participation is counter-indicated, all research and treatment procedures will be terminated.

There is a risk of a loss of confidentiality of personal information as a result of participation in this study. There is a risk of being randomly assigned to a treatment condition that is less effective than the other.

ADEQUACY OF PROTECTION AGAINST RISKS

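### The rule for choosing auxiliary variables screens on treatment discontinuation, which covers only one of the plan's two stated routes to missing outcomes

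*Combined protocol and SAP*

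**What the plan says.** All of the following are in the combined protocol and SAP.

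- **Section D, Missing Data, the rule.** "Baseline differences also will be explored between treatment completers and those that discontinue". If differences are found, "these covariates will then be included in the final model as auxiliary variables to improve the plausibility of assuming data is MAR".
- **Same section, sources of missing data.** Missing data "will occur if participants discontinue treatment prior to the end of the study or do not complete an outcome measure". That is two routes.
- **Same section, retention.** In general "participants will remain in the study unless consent is withdrawn or if there are concerns regarding participant safety". For those who do not finish 12 sessions in 18 weeks, "treatment will be discontinued and follow-up assessments will be completed".
- **Section E, Potential Risks.** If a participant wants to stop because of distress, or a clinician judges participation contraindicated, "all research and treatment procedures will be terminated".
- **Section D, assessment procedures.** Assessments are scheduled apart from therapy sessions and may be done in person, by post or online.
- **Section D, Efficacy Measures Analyses.** The primary model adjusts for the baseline value of the outcome. It also adds further covariates, given as examples: age, number of comorbidities, race, sex, combat theatre, number of sessions and specific DST received.

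No variable-by-variable comparison of participants with and without an observed outcome is planned.

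**The concern.** Auxiliary variables are there to make missing-at-random (MAR) more credible. MAR is a statement about who has a missing score, so the useful candidates are variables related both to a missing score and to the outcome. The rule asks a different question: who stopped therapy.

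The plan's own text separates the two events. A participant who exceeds 18 weeks is a discontinuer but should have outcomes. A participant who finishes therapy can fail to return a form. The screen puts the first on the missing side and the second on the observed side. Both errors dilute the contrast for a variable that predicts missing scores, so such a variable can fail to enter. If it is also related to the outcome, and missingness depends on it differently in the two arms, the estimated arm difference behind the non-inferiority bound is biased.

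**Working it through.** The plan gives no figure to reproduce here: it states no expected missing-outcome rate, and no test or cut-off for the screen. Everything below is illustration under stated assumptions.

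**Inputs from the document.** N = 306. Pilot completion was 12 of 15 and 21 of 29, so (3 + 8)/44 = 25% discontinued.

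**Assumptions for step 1.** A baseline variable differs by 0.5 SD between participants with missing and observed outcomes. It is linked to discontinuation only through missingness. The test is two-sided at 5%.

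**Step 1: chance of selecting the variable.** Let a and b be the proportions with a missing outcome among discontinuers and completers.

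- Planned screen: expected difference = 0.5 × (a − b); SE = √(1/76.5 + 1/229.5) = 0.132.
- Missing-versus-observed screen: difference = 0.5; overall missing m = 0.25a + 0.75b; SE = √(1/(306m) + 1/(306(1 − m))).
- Power = Φ(diff/SE − 1.96) + Φ(−diff/SE − 1.96).

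Example, a = 0.6 and b = 0.1. Planned: 0.25/0.132 = 1.89, power 47%. Alternative: m = 0.225, SE = 0.137, 0.5/0.137 = 3.65, power 95%.

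| a | b | Planned screen | Missing vs observed |
|---|---|---|---|
| 1.0 | 0 | 97% | 97% |
| 0.8 | 0.05 | 81% | 96% |
| 0.6 | 0.10 | 47% | 95% |
| 0.4 | 0.10 | 21% | 91% |
| 0.2 | 0.10 | 7% | 82% |
| 0.1 | 0.1 | 5% | 75% |

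The two screens agree only when discontinuation and missingness coincide. At the other end the planned screen works at chance level.

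**Step 2: bias if a relevant variable W is left out.** Assume W drives missingness in one arm only, with logistic log-odds 0.5 to 1 per SD, 20 to 35% missing, and partial correlation .3 to .5 with the outcome. Bias in the arm difference = partial correlation × |mean of W among the observed|.

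- Low: log-odds 0.5, 20% missing: 0.3 × 0.096 = 0.03 SD.
- Middle: log-odds 0.75, 27.5% missing: 0.4 × 0.187 = 0.075 SD.
- High: log-odds 1, 35% missing: 0.5 × 0.292 = 0.15 SD.

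With the same log-odds (0.75) in both arms but 20% against 35% missing, the biases do not quite cancel: 0.4 × (0.235 − 0.138) = 0.04 SD.

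**Step 3: large-sample simulation.** The outcome was adjusted for its baseline, W had coefficient 0.4, about 24 to 27% were missing, and missingness among completers depended on W. Without W, the bias in the arm difference was about 0 when the mechanism was the same in both arms, 0.05 SD when it acted in one arm, and 0.07 SD when it ran in opposite directions. Including W removed it.

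**The case against.** A reader might infer that discontinuation is not what makes outcomes missing, so that the screen is beside the point. The documents do not support that. The Missing Data section lists discontinuation as one of the two causes, and Potential Risks ends research procedures for some who stop. Completed follow-up after treatment stops is stated outright only for the 18-week rule. The screen is a partial proxy, and where missingness follows discontinuation closely it works well (first rows of the table).

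The other side has further points that stand:

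- The primary model already holds the baseline outcome and several covariates whatever the screen shows. The list is only illustrative, however. It omits the other baseline primary scores, IIRS and principal diagnosis.
- The plan names no test or threshold, so low screening power is a consequence of the assumed 5% test.
- Large bias and a weak screen need not occur together. If missingness tracked discontinuation, a one-arm log-odds of 1 would give a pooled baseline difference of about 0.42 SD, which the planned screen would detect with roughly 86 to 94% power. The problem lies where the two events diverge.
- No passage predicts missingness that differs by arm. The secondary hypothesis does expect discontinuation to differ, so unequal missingness is possible.

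Little's test and the completer and per-protocol comparisons do not fill the gap. The first is an overall test and the others change the analysis set. None is used to choose auxiliary variables.

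**Conclusion.** The point holds in limited form: the selection rule does not fit its stated MAR purpose, because it screens on one of two routes to missing data and misclassifies participants in both directions. The likely effect on the arm difference is modest, about 0.03 to 0.15 SD with 0.075 SD in the middle case. That rests on a one-arm mechanism and on the assumed missingness rates, log-odds and partial correlations. It is near zero if mechanism and rate are the same in both arms.

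Against the 0.5 SD margin in the sample size section, the middle case is 0.075/0.5 = 15% of the margin. The efficacy section states a margin of 0, against which a bias of this size could matter more. That conflict is a separate issue. It would go too far to conclude that the primary analysis is invalid or that bias is expected. The change is worth making because it is nearly free.

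**What to change.** In the Missing Data section:

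1. Replace the completer-versus-discontinuer comparison with a comparison of participants with and without each primary outcome, at post-treatment and at 6 months, by arm. This is the main change, because it addresses missed assessments directly.
2. Enter a fixed auxiliary set regardless of any test, from baseline data already collected: all baseline primary scores, IIRS, principal diagnosis, number of comorbidities and age.
3. Reconcile the Missing Data section with Potential Risks on whether outcomes are collected after treatment stops. The two passages currently read differently.

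The cost is a wording change, slightly more analysis work and a larger model. No new data are needed, and auxiliary variables do not alter the estimand.

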For all study outcomes (ADIS-5, IIRS, PCL-5, PDSS, PHQ-9, and STICSA), Veterans will be randomly assigned (1:1) to the TBT and specific DST conditions. The power analysis was calculated to be powered at 80% with a Bonferroni-corrected 1-tailed $\alpha = .006$ (.025/4 primary outcomes) to detect non-inferiority for TBT in comparison to the aggregated DST effect. Meta-analyses for CBT for MDD, CPT for PTSD, and CBT for PD/AG reveal large treatment effects (CBT for MDD bias-adjusted $g = .53$; Cuijpers et al., 2013; CPT for PTSD in military personnel $g = 1.33$; CBT for PD $g = 0.35$; Hofmann & Smits, 2008). Thus, the average effect size for DSTs was expected to range from small-to-medium to large. A power analysis was conducted using procedures recommended by Chow, Shao, and Wang (2017), Flight and Julious (2014), and Julious (2004) as well as recommendations by the United States Food and Drug Administration and the European Medical Association (Food and Drug Administration, 2017). An important topic in non-inferiority designs is selection of the “appropriate” prespecified non-inferiority limit. Current best practice involves selecting a non-inferiority margin that is not greater than the smallest effect size expected for the DSTs in comparison to a control condition. As a tradeoff between sample size needs and feasibility of recruitment, we conducted power analysis setting the non-inferiority margin to 0.5, indicating that we would consider TBT non-inferior to the DSTs if TBT were to perform less than half a standard deviation worse than the DSTs. We set the expected group different to 0.3 given our pilot data demonstrating that TBT outperforms DSTs by this margin across primary outcome variables. Using procedures recommended by Chow, Shao, and Wang (2017) for non-inferiority designs, which utilize the pre-specified non-inferiority margin (here prespecified as $\Delta d = 0.5$) and the estimated effect in the active comparison treatment ($d = 0.3$), we determined that 144 participants (72 per cell) would be needed. However, this does not account for potential attrition or for potential design effect issues involving therapist effects or for potential missing data related to telehealth delivery of services. To account for possible attrition and missing data as well as the potential influence of design effects, we increased the sample size to 306 participants based on the data available to date. Based on pilot data, we expect to find large within-person effects ($d \geq .80$) for TBT, indicating 4/5ths of a SD reduction in each of the primary outcome measures. This sample size would leave us powered to detect small-to-medium within-person effect sizes.

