The continuous measures included measures of disorder severity scales (ADIS-5), disorder-specific symptomatology (PCL-5, PDSS, PHQ-9, and STICSA), general related symptomatology (STISCA), and quality of life and impairment (IIRS). Of these variables, the PCL-5, PDSS, PHQ-9, and STICSA are the primary outcomes of interest. All other analyses will be conducted in an exploratory fashion to inform future studies and compare findings to previous studies ([name], 2014; [name] et al., 2017; 2019). Parameter estimates to calculate the effect size difference will be arrived at using three-level (measurement occasions nested within participants nested within assigned treatment condition) generalized mixed-effects regression models (MRM). MRM is a method of repeated measures analyses that allows for modeling of continuous and categorical independent and dependent variables and for appropriate modeling of covariance structures when observations are correlated across time and/or across condition. This analytic approach fully captures variability in outcomes across multiple follow-up assessments and accounts for any potential effect of the group to which a participant is assigned and is thus preferred over methods that collapse data over time. We will calculate between-group treatment differences as Cohen's d, based on the effect of treatment condition on the intercept parameter when the model is centered on post-intervention and on the effect of treatment condition on the intercept parameter when the model is centered on month 6. We prespecified the non-inferiority margin (d) to be 0 (indicating we expected TBT to be at least equivalent to the aggregate DST effect) and the one-sided CI for our four primary analyses at $\alpha = .006$. In the primary analyses of outcome variables, we will covary for the baseline value of the variable of interest. We also will include the linear effect of time as well as a time by condition interaction effect to determine whether treatment differences (or lack thereof) were stable from post-intervention through the follow-up. Additional covariates (e.g. age, number of psychiatric comorbidities, race, sex, combat theatre, number of treatment sessions, specific DST received) will be added to the model to adjust for putative confounding variables. Effect size CIs that do not contain 0 provide evidence in support of noninferiority for TBT. The primary outcome time point is at the end of the active treatment phase and the secondary time point is at the end of the naturalistic 6-month follow-up period. Further, within-subject effect sizes from baseline to post-intervention and to 6-month follow-up also will be calculated within the TBT condition to quantify TBT-specific reductions in symptoms. These analyses will be probed to examine potential therapist effects. First, design effects will be calculated for the primary outcome variables. Design effects > 2 are often used as a heuristic to judge when these effects can be problematic.

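### The primary model carries a redundant condition level, while therapist clustering stays out of the bound that decides non-inferiority and no rule covers disagreement with the adjusted analysis

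*Combined protocol and SAP*

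**What the plan says.** All references are to the combined protocol and SAP.

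- **Primary model.** *Efficacy Measures Analyses (Primary Aim)* specifies "three-level (measurement occasions nested within participants nested within assigned treatment condition) generalized mixed-effects regression models (MRM"). The arm difference is a Cohen's d "based on the effect of treatment condition on the intercept parameter when the model is centered on post-intervention", with a time-by-condition term as well. Condition is therefore both the top level and the tested fixed effect. Each of the four primary outcomes is judged by a one-sided bound at .006. Therapist is neither a level nor among the covariates given as examples.
- **Therapist effects.** These come afterwards in the same section. Design effects are calculated for the primary outcomes, with the remark "Design effects > 2 are often used as a heuristic to judge when these effects can be problematic". A sensitivity analysis with the Mplus complex estimator then follows, whatever the design effect turns out to be. Nothing says what happens to the conclusion if it disagrees with the primary result.
- **Sample size.** *Sample Size Determination for Proposed Analyses* says of its base figure of 144 that "this does not account for potential attrition or for potential design effect issues involving therapist effects". To cover attrition and missing data, "as well as the potential influence of design effects, we increased the sample size to 306 participants". No ICC, therapist count or design effect is given.
- **Estimation.** *Missing Data*: "Missing data for the MITT analysis set will be accounted for using full information maximum likelihood (ML").

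**The concern.** A random level earns its place by representing units that are sampled and that share variation. Condition has two units, and its effect is the quantity under test, so a variance between conditions cannot be separated from the fixed effect. Participants treated by the same therapist do share variation, and the plan says so in two sections, yet the standard error behind the deciding bound ignores it.

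Raising N to 306 adds power. It does not correct a standard error that leaves out clustering.

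At stake is the error rate of the non-inferiority claim: the chance of passing TBT when its true difference sits exactly at the margin. Whether that exceeds .006 depends on how therapists are allocated, which the documents do not state.

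**Working it through.** **The plan's own figures.** Alpha is .025/4 = .00625, which the plan gives as .006; z(.006) = 2.512. There is no planned therapist design effect to reproduce. The plan gives only the total inflation, 306/144 = 2.125, not split between attrition, missing data and therapist effects. (The stated inputs do not reproduce 144: a distance of 0.5 + 0.3 = 0.8 gives 36 per arm, 72 in total. That is a separate matter, and nothing below uses 144.)

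**Step 1: the third level.** With condition fixed, 153 per arm and residual variance 1, adding a between-condition variance τ² changes the maximised log-likelihood by −ln(1 + 153τ²):
- τ² = 0: 0
- τ² = .01: −ln(2.53) = −0.93
- τ² = .10: −ln(16.3) = −2.79

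The maximum is at zero, so the fitted model has two levels. In a simulated repeated-measures data set the estimated arm effect was the same at every τ² tried, so the level does not bias it.

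**Step 2: error of a bound that ignores therapist.** Assumptions: total variance 1, equal caseloads, one post-treatment score per participant, N = 306. The therapist count J (total), the ICC and the variances are also assumed, because the documents give none.

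*Nested (each therapist in one arm).* DE = 1 + (N/J − 1) × ICC; error = 1 − Φ(2.512/√DE).

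| J | ICC | DE | Error |
|---|---|---|---|
| 20 | .01 | 1.14 | .0094 |
| 20 | .05 | 1.72 | .0275 |
| 10 | .01 | 1.30 | .0137 |
| 10 | .05 | 2.48 | .0553 |

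*Crossed (each therapist in both arms).* With u the therapist variance and v the variance per therapist-arm cell, Var(difference) = 2v/J + 4(1 − u − v)/N, against the assumed 4/N. The ratio R of the two replaces DE.

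| J | u | v | R | Error |
|---|---|---|---|---|
| any | .01 | 0 | .99 | .0058 |
| any | .05 | 0 | .95 | .0050 |
| 10 | .05 | .01 | 1.09 | .0081 |
| 10 | 0 | .02 | 1.29 | .0134 |
| 6 | .05 | .01 | 1.20 | .0108 |
| 6 | 0 | .02 | 1.49 | .0198 |

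Simulation with 200,000 replicates agreed: .056 for nested J = 10, ICC .05; .0053 to .0060 for crossed v = 0; .0117 to .0204 for crossed J = 6, v .01 to .02.

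**Step 3: the other sample size.** *Randomization Procedures* gives 108 per arm, which is 216 in total. At N = 216 the worst nested case has DE = 1 + (21.6 − 1) × .05 = 2.03 and error .039. The worst crossed case in the table falls to .015.

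**Step 4: power with therapist in the model.** N = 306 and margin 0.5, because in the sample-size section "we conducted power analysis setting the non-inferiority margin to 0.5". The analysis section instead states "We prespecified the non-inferiority margin (d) to be 0". That conflict is a separate point; the error rates in Step 2 hold at whichever margin is used.
- *No clustering:* SE = √(4/306) = .114; power at a true difference of 0 is Φ(.5/.114 − 2.512) = .969.
- *Crossed, random intercept only, u = .05, v = 0:* SE = √(4 × .95/306) = .111; power .976.
- *Nested, noncentral t with J − 2 df:* with J = 20 and ICC .01, the critical value is 2.79, SE is .122, and power is .89 at a true difference of 0 and over .99 at the planned 0.3 advantage. With J = 10 and ICC .05, the critical value is 3.23, SE is .180, and power is .39 and .85.

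**The case against.** The strongest reply is that therapist effects are largely handled already. They are named in the sample-size section, design effects will be calculated, and an adjusted analysis is run unconditionally. On this view one sentence saying which result decides would be enough. Much of this stands, and the gap is narrow. That sentence would close the decision gap, but it would leave a level that does nothing in the model, and cluster-robust standard errors are unreliable with few therapists.

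A second reply is that therapists probably treat in both arms. *Treatment Training and Fidelity* describes weekly supervision across all four protocols. The contamination steps in *Randomization Procedures* do not include separate therapists. That section also limits knowledge of assignment to the analyst and a single therapist/coordinator role. This leans towards crossing without settling it, since other text speaks of therapists in the plural. If it is right, and the arm difference is constant across therapists, the unadjusted bound is sound. The nested figures therefore should not be read as the expected case.

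A third reply is that a decisive therapist-by-condition term could cost heavy power with no error to correct. That stands. With J − 1 degrees of freedom and no therapist-by-arm variance, power at margin 0.5 and a true difference of 0 would be .86, .68 and .41 with 10, 6 and 4 therapists, against .97. The fix does not require that term in the primary model.

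A reader might also infer that the design-effect threshold of 2 decides whether clustering is adjusted for, so that a value below 2 would let it pass. The text does not say so: no analysis depends on the threshold.

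**Conclusion.** The point holds as a specification fault with a conditional consequence. The condition level is redundant but harmless. The substantive gap is that the deciding bound omits the clustering the plan expects, and no rule says what happens if the adjusted analysis differs.

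Against a nominal .006 at N = 306, the error of the unadjusted bound is:
- .005 to .006 if therapists are crossed with arm and there is no therapist-by-arm variance (no inflation);
- about .008 to .013 with 10 therapists, or .011 to .020 with 6, if they are crossed with variance .01 to .02;
- .009 to .055 if 10 to 20 therapists are nested in arm and the ICC is .01 to .05.

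Every clustering input is an assumption. The errors are somewhat smaller at N = 216, and the two sample sizes must be reconciled.

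A reader might infer that the non-inferiority test is invalid, or that its error is several times nominal. The documents do not support that: it follows only under nesting or appreciable therapist-by-arm variance, and neither is stated. The change is worth making before analysis. Confidence in its practical size is medium.

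**What to change.** 1. In *Efficacy Measures Analyses (Primary Aim)*, replace the condition level with therapist. For example: *repeated assessments within participants, participants within therapists; condition as a fixed effect only; random intercept for therapist; small-sample degrees of freedom if therapists are nested in arm. The bound from this model decides non-inferiority.*
2. State the planned number of therapists and whether each treats in both arms.
3. If they do, keep the random intercept in the primary model and report a therapist-by-condition term as a sensitivity analysis. The intercept alone does not remove inflation from therapist-by-arm variance. Making that term decisive is the sponsor's choice, to be made once the therapist count is known.
4. Keep the model without therapist as a sensitivity analysis, and report the design effect as description.
5. Restate power for the allocation actually planned, after reconciling 306 with 108 per arm.

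**Cost.** SAP wording and a revised power statement. No new data are needed: *Procedures* assigns every randomised participant to a project therapist, and the planned sensitivity analysis already requires therapist identity. If therapists cross arms, the random intercept costs nothing to speak of (.976 against .969). If they are nested, the bound is wider and power falls as in Step 4, to .39 at a true difference of 0 in the worst case shown. The apparent extra power of the unadjusted bound in that case comes from an understated standard error.

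### The plan prespecifies two different non-inferiority margins, 0.5 SD for the sample size and 0 for the primary analysis, and does not say which one decides the trial

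*Combined protocol and SAP*

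**What the plan says.** The opening statement of goals and the Objective under RCT of TBT both describe a non-inferiority comparison of TBT with DSTs.

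Sample Size Determination for Proposed Analyses says that "we conducted power analysis setting the non-inferiority margin to 0.5" and explains that "we would consider TBT non-inferior to the DSTs if TBT were to perform less than half a standard deviation worse than the DSTs". It repeats 0.5 as the prespecified margin when deriving 72 per cell, at one-sided .006 (.025/4) and 80% power, with an expected group difference of 0.3. It then adds: "we increased the sample size to 306 participants based on the data available to date". The same section describes best practice as "selecting a non-inferiority margin that is not greater than the smallest effect size expected for the DSTs" against a control condition. The DST effects it cites are 0.53 (MDD), 1.33 (PTSD) and 0.35 (PD).

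Efficacy Measures Analyses (Primary Aim) gives a different margin: "We prespecified the non-inferiority margin (d) to be 0 (indicating we expected TBT to be at least equivalent to the aggregate DST effect"). It refers to "the one-sided CI for our four primary analyses" at .006 and gives the decision rule as "Effect size CIs that do not contain 0 provide evidence in support of noninferiority for TBT". It states neither the sign convention for d nor which confidence bound is compared with the margin.

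**The concern.** The margin and the confidence bound together are the primary decision rule of a non-inferiority trial, and here they apply to each of the four primary outcomes. With two margins both called prespecified, the plan gives two verdicts for the same data over a wide range of results.

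The zero cannot simply be read as a slip for 0.5. It appears once with a rationale and again in the operative rule, so it may be a deliberate, stricter choice. In that case the primary analysis is a superiority test: the power calculation does not apply to it, and two equally good treatments would almost never pass. If 0.5 was meant, the analysis section as written would reject results that the sample size section calls non-inferior.

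The missing sign also matters in practice. Lower scores are better on the symptom scales, so a raw treatment coefficient that favours TBT could be negative.

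**Working it through.** **Inputs.** From the sample size section: one-sided alpha .006, power 80%, margin 0.5, expected difference 0.3 in TBT's favour. From the analysis section: margin 0. Evaluable numbers per arm are not given, so three values are used: 72 (the figure before inflation), 108 (Randomization Procedures) and 153 (306/2, no loss). SD is 1, so differences are in units of d, and d > 0 favours TBT. z(.994) = 2.512 and z(.80) = 0.842.

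**The plan's own figure.** n per arm = 2 × ((2.512 + 0.842)/(margin + d))².
- Margin 0.5, TBT better by 0.3: 2 × (3.354/0.8)² = 35.1, so 36 per arm (72 in total).
- Margin 0.5, equal arms: 2 × (3.354/0.5)² = 90.0, so 90 per arm.

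Neither gives 72 per cell. The first gives 72 in total, so a total may have been used as a per-arm figure, but that is inference. The section also describes the 0.3 in two ways, as TBT's advantage and as the effect in the comparison treatment.

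**Power per outcome.** Φ((margin + d) × √(n/2) − 2.512). For example, margin 0, d = 0.3, n = 153: 0.3 × 8.746 − 2.512 = 0.112, and Φ = 54%.

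| Margin | True d | n = 72 | n = 108 | n = 153 |
|---|---|---|---|---|
| 0.5 | 0 | 69% | 88% | 97% |
| 0.5 | 0.3 | 99% | >99.9% | >99.9% |
| 0 | 0 | 0.6% | 0.6% | 0.6% |
| 0 | 0.3 | 24% | 38% | 54% |

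For 80% power at margin 0 and d = 0.3, the formula above gives 2 × (3.354/0.3)² = 250 per arm.

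**Where the rules disagree.** Margin 0 needs an observed d above 2.512 × SE. Margin 0.5 needs an observed d above −0.5 + 2.512 × SE. With SE = √(2/153) = 0.114, the range that passes 0.5 and fails 0 is −0.21 to +0.29. At 108 per arm it is −0.16 to +0.34, and at 72 it is −0.08 to +0.42. The width is always 0.5, the gap between the margins; n only moves its position. At 153 per arm, the chance of landing in it is 96% with equal arms and 46% at d = 0.3.

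**What the simple model leaves out** (margin 0, d = 0.3, starting from 153 per arm; all rates are assumptions).
- Baseline adjustment with correlation r multiplies the variance by 1 − r². For r = 0.5, 0.3 × √(153/(2 × 0.75)) − 2.512 = 0.518, giving 70%; r = 0.6 gives 78%.
- Attrition and clustering together give effective n = 153 × retention / design effect. With 70% retained and a design effect of 2, n = 53.6 and power is 17%. With 80% retained and a design effect of 1.2, n = 102 and power is 36%.

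**The margin against the plan's cap.** The smallest DST effect cited is 0.35, and 0.5 exceeds it. At margin 0.35 with equal arms, power is 34%, 52% and 71% at 72, 108 and 153 per arm, without baseline adjustment. At 153 per arm, adjustment with r = 0.5 to 0.6 would raise 71% to about 85–91%.

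**The case against.** The analysis section is not wholly without direction. It calls the interval one-sided, expects TBT to be at least equivalent, and speaks of support for TBT. A reader might infer that an interval lying entirely on the side where TBT is worse would count as non-inferiority. That reading is strained and the text around the rule does not support it. What is missing is narrower: the sign of d and the named bound.

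A reader might also infer that the analyst could choose the margin after seeing results, because an analyst knows the assignments and post-treatment analyses are scheduled from month 24, before treatment ends. The documents do not say who fits the outcome models or that those analyses compare arms, so this is not established and the point does not need it.

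The simple power figures ignore the planned baseline covariate, which could lift 54% to 70–78%. This stands as a caveat on size. It leaves the conflict intact, since the range of disagreement stays 0.5 SD wide.

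Finally, the sample size section openly gives its reason for 0.5, a tradeoff between sample size and feasibility, and the 0.35 comes from PD alone, whereas the trial is powered "to detect non-inferiority for TBT in comparison to the aggregated DST effect". So 0.35 is not shown to be the binding cap. The plan should still say how 0.5 meets its own principle.

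**Conclusion.** The point holds and must be fixed: the two sections prespecify different margins and nothing reconciles them. Under the analysis section's rule the trial tests superiority. It would then pass equally effective arms 0.6% of the time per outcome, against 97% under the margin used for sizing, and 54% against over 99.9% if TBT is better by 0.3. These figures assume a normal approximation, SD 1, 153 evaluable per arm, and no attrition, clustering or baseline adjustment. The assumptions shift the percentages considerably (17% to 78% for margin 0 at d = 0.3 across the cases shown). The contradiction itself needs none of them.

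The percentages are for one outcome. They should not be read as trial-level success probabilities, because alpha is split over four outcomes and the sample size section does not require all four to succeed. Nor do they show that 306 is too few: that depends on which margin is chosen and on loss, clustering and correlation values that the plan does not give.

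**What to change.** Before any comparison of outcomes by arm:

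1. State one margin, identical in the sample size and primary analysis sections.
2. Replace the decision rule in the primary analysis section with: *TBT is non-inferior on an outcome if the lower one-sided 99.4% confidence bound for d (scored so that positive favours TBT) lies above minus the margin.* If 0 is kept as the criterion, call it superiority and align the stated aim and power with it.
3. Justify the chosen margin against the plan's own cap, saying whether the 0.35 for PD or an aggregated DST effect applies.
4. Restate per-outcome power for that margin, with explicit assumptions for attrition, clustering and baseline adjustment taken together. In the same restatement, correct the 72 per cell.

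The rule change is wording only and needs no new data. The cost is that the restated power may be below 80%, most clearly if the margin is tightened or 0 is kept, and the plan would have to say so.
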